1. INTRODUCTION

This document describes the statistical methods and data presentations to be used in the summary and analysis of data from Protocol BCX1812-306. Background information is provided for the overall study design and objectives. The reader is referred to the study protocol and case report forms (CRFs) for details of study conduct and data collection, respectively.

This document describes all analyses of safety, clinical effectiveness, pharmacokinetics (PK) and virology analyses. PK and virology analyses will be written as separate reports from the clinical study report.

1.1. STUDY OVERVIEW

Protocol BCX1812-306 is a multicenter, single-arm, open-label study to evaluate the safety, PK, and effectiveness of a single dose of peramivir administered intravenously (IV) in elderly subjects (≥ 65 years of age) with acute uncomplicated influenza and in younger subjects (< 65 years of age) with acute uncomplicated influenza who are at higher risk for influenza complications. Elderly subjects will not be classified as high or low risk and will be captured as elderly only.

Approximately 120 subjects will be enrolled in this open-label study (a minimum of 80 elderly subjects will be enrolled). A subject's duration of participation in this study is expected to be 14 days and will include up to 4 clinic visits. It is expected that most subjects will have the Screening visit and the Day 1 Treatment visit on the same day. Following treatment on study Day 1, subjects will undergo follow-up assessments on Days 3, 7, and 14 in the clinic. Subjects will be discharged from this study on Day 14. Additional unscheduled visits may be required for subjects who report symptoms of influenza of moderate or severe intensity at Day 14 or have persistent adverse events (AEs) and/or treatment-emergent laboratory findings that require medical monitoring or management.

Eligible subjects will have a positive influenza Rapid Antigen Test (RAT) and/or a Food and Drug Administration (FDA) approved polymerase chain reaction (PCR) test and at least one clinical sign or symptom consistent with influenza OR clinical signs and symptoms consistent with acute influenza infection consisting of an oral temperature $\geq 37.8^{\circ}\text{C}$ / 100°F with at least one respiratory symptom of at least moderate severity (cough or rhinitis) and at least one constitutional symptom of at least moderate severity (myalgia, headache, feverishness, or fatigue).

Subjects will receive a single IV dose of 600 mg peramivir (or less if renally impaired), which will occur over 15 to 30 minutes.

An adequate nasal swab specimen will be collected from all enrolled subjects at Baseline (predose) for virus subtype identification and quantitative virologic assessments and at the follow-up assessments on study Days 3, 7, and 14.

Specimens obtained from all subjects on Day 1 and the last specimen that yields influenza virus on culture will also be assessed for susceptibility to neuraminidase inhibitors. A central laboratory will perform all virologic assessments.

Up to 3 blood samples will be drawn to obtain plasma samples for drug concentration determinations, where possible, during the following time periods, beginning from the end of dosing until release from the site on the day of dosing:

- One time point immediately following completion of the infusion
- One time point from 30 minutes to 1 hour post-infusion
- One time point from 1 hour to 3 hours post-infusion

AEs and concomitant medications will be monitored at each scheduled visit from the Screening assessment to final study visit. Clinical laboratory investigations (chemistries, hematology, and urinalysis) will be collected at Baseline, Day 7, and Early Withdrawal visits. Safety and tolerability will be evaluated through assessments of AEs, laboratory analyses (clinical chemistry, hematology, and urinalysis), vital signs, and physical examinations at the time points indicated in the schedule of assessments (see Section 1.2).

All subjects or their caregivers will record the following information in a Subject Diary:

- Assessment of the presence and severity of each of 7 symptoms of influenza on a 4-point severity scale (0, absent; 1, mild; 2, moderate; 3, severe) at Screening, then twice daily through Day 13, and prior to the subject's clinic visit on Day 14 or until each symptom is rated as a 0 or 1 for 48 consecutive hours. Diaries will be reviewed at each clinic visit.
- Temperature measurements (oral) will be taken with an electronic thermometer provided by the Sponsor, approximately every 12 hours until temperature normalizes for 48 hours (ie, temperature without antipyretic is $< 37.4^{\circ}\text{C}/99.4^{\circ}\text{F}$ orally for 4 consecutive measurements). With the exception of the Screening/ Baseline measurement, all temperature measurements will be obtained at least 4 hours after, or immediately before, administration of oral acetaminophen or other antipyretic medications, if taken.
- The type, date, and time of medications used for the symptomatic treatment of influenza-related symptoms.
- Assessment of the subject's ability to perform usual activities using a 0 to 10 visual analog scale once daily through Day 14, where 0 = Unable to perform usual activities at all, and 10 = Able to perform all usual activities fully.

1.2. SCHEDULE OF EVENTS/STUDY VISITS

Assessments	Screening ¹	Baseline ¹ (Pre-dose)	Day 1 Treatment Day ¹	Day 3	Day 7 (+2 days)	Day 14 (+3 days) / End of Study	Early Withdrawal
Informed Consent	X						
Inclusion/Exclusion Criteria	X						
Medical History/Physical Exam	X			X ⁶	X ⁶		
Vital Signs ²	X			X	X	X	X
Body Temperature ³	X	X	X	X	X	X	X
Clinical Chemistries and Hematology ⁴		X			X		X
Urinalysis ⁴		X			X		X
Pregnancy Test (Urine or Serum)	X					X	X
Assessment of Influenza Symptoms ⁵	X		X	X	X	X	X
Ability to Perform Usual Daily Activities ⁵		X		X	X	X	X
Influenza Related Complications (IRC) ⁷	X			X ⁷	X	X	X
Concomitant Medications Review	X		X	X	X	X	X
Subject Diary Review			X	X	X	X	X
Pharmacokinetic (PK) Sampling			X				
Serum Sample for Influenza Antibody Analysis ⁸		X		X	X		X
Swabs for Virology Analysis		X		X	X		X
Rapid Antigen Test (RAT) or FDA-approved PCR Test for Influenza A and B on Nasal Specimen	X						
Study Drug Administration			X				
Adverse Events ⁹	X	X	X	X	X	X	X

- 1 It is expected that the date of Screening, Baseline, and Day 1 (date of study drug administration) will be the same. Day 1 consists of pre and post-dose assessments.
- 2 Vital sign measures will include blood pressure, pulse rate, and respiration rate. Vital signs will be recorded once during Screening, and vital signs will be taken once on remaining study visit days.
- 3 The investigator will record oral body temperature at Screening. Thereafter, the subject or care giver will record oral body temperature approximately every 12 hours in the Subject Diary until temperature normalizes for 48 hours (ie, temperature without antipyretic is $< 37.4^{\circ}\text{C} / 99.4^{\circ}\text{F}$ orally for 4 measurements).
- 4 Clinical laboratory assessments performed at Screening are for the purpose of establishing a baseline. Subjects may be enrolled and begin treatment with study drug prior to receiving results. These labs may be done at any visit if necessary for subject management or adverse event monitoring purposes.
- 5 Influenza signs and symptoms will be recorded by the study personnel at Screening, then by the subject or care giver twice daily beginning on Day 1 through Day 13, and prior to the subject's clinic visit on Day 14 or until each symptom is 0 or 1 for 48 hours.
- 6 Perform a targeted physical exam on Day 3 and Day 7
- 7 If an influenza related complication (IRC) is suspected the subject will be instructed to return to the clinic as appropriate to confirm the presence or absence of IRCs.
- 8 A single serum specimen will be collected, where possible, pre-dose on Day 1, Day 3 and on Day 7 for analysis of influenza antibody titers.
- 9 Adverse events are to be collected from the time of informed consent through the follow-up period ending on Day 14.

1.3. GLOSSARY OF ABBREVIATIONS

AE	adverse event
CRF	case report form
FDA	Food and Drug Administration
ITT	intent-to-treat
ITTI	intent-to-treat infected
IV	Intravenous
PCR	polymerase chain reaction
PK	pharmacokinetic
RAT	rapid antigen test
RT-PCR	real time polymerase chain reaction
SAE	serious adverse event
TCID ₅₀	Tissue-culture infective dose ₅₀
TEAEs	treatment-emergent adverse events

2. OBJECTIVES

The primary objective is to evaluate the safety and tolerability of peramivir administered IV in elderly subjects with acute uncomplicated influenza and in subjects with acute uncomplicated influenza who are at higher risk for influenza complications.

The secondary objectives for this study are as follows:

- To describe the PK of IV peramivir in elderly and high-risk subjects with acute uncomplicated influenza
- To evaluate the effectiveness of IV peramivir in elderly and high-risk subjects with acute uncomplicated influenza
- To evaluate the incidence of influenza complications, specifically otitis media, sinusitis, bronchitis, or pneumonia requiring antibiotic use diagnosed after initiation of treatment.

3. GENERAL STATISTICAL CONSIDERATIONS

3.1. SAMPLE SIZE AND POWER

The study is designed to evaluate the safety, PK, and effectiveness of IV administration of

peramivir in subjects ≥ 65 years of age with influenza infection and in subjects with influenza infection who are at an increased risk of influenza complications. A sample size of up to 120 subjects, and a minimum of 80 elderly subjects (aged ≥ 65 years), is considered adequate to evaluate the stated objectives. A formal sample size calculation was not performed.

3.2. RANDOMIZATION AND MASKING

As this is a single-arm, open-label study, randomization and masking are not applicable.

3.3. HANDLING OF DATA

3.3.1. Strata and Covariates

There will be no stratification for this study.

3.3.2. Examination of Subject Subsets

All analyses will be presented by age group (≥ 65 years, 65-75 years, >75 years, and < 65 years). Time to resolution of fever, time to alleviation of symptoms, change in tissue-culture infective dose 50 (TCID₅₀), viral shedding, real-time PCR (RT-PCR) results, and change of influenza virus susceptibility to neuraminidase inhibitors analyses will be presented by age group and viral subtype at Screening. Additional subgroups defined based on risk of complications may be evaluated.

3.3.3. Multiple Testing and Comparisons

All analyses will be conducted without adjustments for multiple testing.

3.3.4. Missing Data and Outliers

Every effort will be made to obtain required data at each scheduled evaluation from all subjects who have been enrolled. No attempt will be made retrospectively to obtain missing subject reported data (such as influenza symptom severity assessments and temperature) that has not been completed by the subject at the time of return of the subject diary to the investigative site. In situations where it is not possible to obtain all data, it may be necessary to impute missing data, as described in the following paragraph.

In assessing the effectiveness endpoint of time to alleviation of symptoms, for subjects who withdraw or who do not experience alleviation of symptoms, missing data will be censored using the date of subject's last non-missing assessment of influenza symptoms. For the subject diary data, the following data conventions will be utilized. Diary completion times will use a 24-hour clock. Missing diary completion times will be imputed as 11:59 for diary entries designated as morning and 23:59 for evening and daily reported values. Entries with values exceeding the 24-hour clock will be handled on a case-by-case basis and reviewed by a member of the clinical project team

prior to implementation. In general, values recorded between 24:01 – 24:59 will be interpreted as values past midnight and will be implemented as such. Values recorded as 60:00, 70:00, and 80:00 will be interpreted as 06:00, 07:00, and 08:00, respectively. Should additional data conventions be required, these will be documented in the derived variable specifications and in the final clinical study report. Other secondary effectiveness endpoints with time to event data will be censored using the date of subject's last non-missing assessment of the given endpoint.

Unless otherwise specified, no other missing data will be imputed.

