#### 13.7.4. Missing Data

Every effort will be made to obtain required data at each scheduled visit from all subjects who have been enrolled. In situations where it is not possible to obtain all data, it may be necessary to impute missing data. In assessing the time to event endpoints, subjects who withdraw or never achieve resolution/alleviation, missing data will be censored using the date of subject's last non-missing assessment. Additional details on the handling of missing data will be presented in the SAP.

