5.2.2. Effectiveness Analyses

A subject's oral temperature taken by subjects and recorded in the diary by subjects/caregivers will be summarized by age group and overall by study visit. A subject has Resolution of Fever if he/she has an oral temperature $< 37.4^{\circ}\text{C}/99.4^{\circ}\text{F}$ oral and no antipyretic medications have been taken for at least 12 hours. The time to resolution of fever will be estimated for each age group and overall using the Kaplan-Meier method with temperature and symptom relief medication information obtained from the subject diary data. Subjects who do not have resolution of fever will be censored at the time of their last non-missing post-baseline temperature assessment.

Alleviation of symptoms will be determined by assessment of symptoms as reported on each Subject Diary. The time to alleviation of symptoms, defined as the time from initiation of study drug until the start of the 21.5 hour period (24 hours less 10%) where all symptoms of influenza are recorded as none or mild, will be estimated overall and for each age group using the Kaplan-Meier method. Subjects who do not experience alleviation of symptoms will be censored at the date of their last non-missing post-baseline assessment.

Change from baseline in \log_{10} TCID₅₀/mL through Day 3, Day 7, and Day 14 will be presented by age group and overall for subjects with positive viral titers at baseline (\log_{10} TCID₅₀/mL > 0.5). A box plot and a histogram of the TCID₅₀/mL values will be presented by visit and age group. In addition, the median change from baseline in TCID₅₀/mL will be presented by visit and age group.

The number and percent of subjects with positive viral titers at baseline (\log_{10} TCID₅₀/mL > 0.5) that shed virus at each visit will be presented by age group and overall.

The RT-PCR results at each visit will be presented by age group and overall for subjects with positive RT-PCR results at baseline.

Change from baseline to last positive value of influenza virus susceptibility to neuraminidase inhibitors will be assessed using virology laboratory tests. Virology laboratory tests will include phenotypic characterizations of influenza virus recovered (hemagglutinin and neuraminidase) and viral susceptibility to zanamivir, oseltamivir, and peramivir, as well as genotyping of virus isolates. These analyses will be presented overall and by age group and viral subtype.

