The development of any post treatment genotypic changes in neuraminidase and hemagglutinin will be assessed by comparison of sequences from baseline and last positive post-treatment virus samples. These analyses will be presented overall and by age group and viral subtype.

The number and percentage of subjects experiencing influenza related complications will be summarized by age group and overall by complication MedDRA version 18.0 preferred term.

The number and percentage of subjects who are hospitalized due to any TEAE and due to any TEAE related to study drug after initiation of treatment will be summarized by age group and overall.

The number of doses of antipyretic medications, as recorded in the subject diary, taken throughout the study and by study day will be summarized by age group and overall.

The change in daily activities will be summarized each day by age group and overall. The ability to perform usual activities is defined as a subject rating of 10 (able to perform all usual activities fully) on the visual analog scale the subject uses to rate his or her current ability to perform usual activities compared with normal ability. The time to return to usual activities will be estimated for each age group and overall using the Kaplan-Meier method. Subjects who do not return to normal activities will be censored at the time of their last non-missing post-baseline assessment.

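### Subjects who die or withdraw because influenza worsens are censored at their last entry, so the late part of the recovery curves is overstated by up to about their share.

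*SAP*

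**What the plan says.** For time to alleviation, SAP 3.3.4 gives one rule: "for subjects who withdraw or who do not experience alleviation of symptoms, missing data will be censored using the date of" the last non-missing assessment of influenza symptoms. It extends the rule: "Other secondary effectiveness endpoints with time to event data will be censored using the date of subject's last non-missing assessment of the given endpoint". SAP 5.2.2 repeats it for alleviation ("Subjects who do not experience alleviation of symptoms will be censored at the date of their last non-missing post-baseline assessment") and for usual activities ("Subjects who do not return to normal activities will be censored at the time of their last non-missing post-baseline assessment"), and fever is censored likewise at the last temperature reading. Protocol 13.7.4 has the same rule: "subjects who withdraw or never achieve resolution/alleviation, missing data will be censored using the date of subject's last non-missing assessment".

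Time to alleviation "will be estimated overall and for each age group using the Kaplan-Meier method", and fever and usual activities use the same estimator. The event comes from the diary: "Alleviation of symptoms will be determined by assessment of symptoms as reported on each Subject Diary". SAP 3.3.4 does not seek missing diary entries after the diary is returned, and it closes with "Unless otherwise specified, no other missing data will be imputed". Neither document gives a separate rule for death or for withdrawal through worsening, and neither plans a sensitivity analysis of the censoring.

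**The concern.** Kaplan-Meier is unbiased only if a censored subject has the same later chance of the event as those still under observation. A subject who dies before alleviation has no later chance. A subject withdrawn because influenza worsens, or because pneumonia develops, probably has a lower one. Protocol 8.3 opens this route: participation can end when continuing would harm the subject or when the subject cannot comply. Censoring such a subject at the last entry in effect spreads that subject's outcome over those who continued, most of whom recover.

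The study has one arm, so no comparator carries the same bias and the estimate is itself the result. Kaplan-Meier plots are listed outputs for fever and alleviation. SAP 3.3.2 also asks for results by age group, including over 75 years, where a few subjects can shift a curve.

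**Working it through.** The plan has no figure to reproduce: there is no sample-size calculation, no test, and no stated rate of death, withdrawal or worsening. The check is therefore an illustration under stated assumptions.

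**Inputs from the documents.** The censoring rule and estimator are as above. About 120 subjects are enrolled, at least 80 of them elderly (SAP 1.1). Follow-up is 14 days. The number in the infected (ITTI) population is not given.

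**Assumed.** A share f stops before the event and does not recover by Day 14. The others recover with survivor function S(t), the probability of not yet having recovered.

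**Step 1: general formula.** If the share f has its last entry at time c, then for t > c:

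- Planned Kaplan-Meier recovery: 1 − [f + (1 − f)S(c)] × S(t)/S(c)
- Actual recovery: (1 − f)(1 − S(t))
- Difference: f × [1 − S(t)/S(c)]

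The difference is never negative and never exceeds f. It approaches f late in follow-up, when S(t) is small.

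**Step 2: Weibull example.** Shape 1.5, median 96 h, c = 48 h, t = 336 h (Day 14), f = 5%.

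- S(48) = exp(−ln 2 × 0.5^1.5) = 0.783
- S(336) = exp(−ln 2 × 3.5^1.5) = 0.0107
- Planned: 1 − (0.05 + 0.95 × 0.783) × 0.0107/0.783 = 98.9%
- Actual: 0.95 × (1 − 0.0107) = 94.0%
- Overstatement: 4.9 points. The median reads 97.3 h instead of about 101 h.

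At f = 1% the same steps give 98.9% instead of 97.9%, and a median about 0.7 h too short. Over medians of 72, 96 and 120 h and stops at 24, 48 and 96 h, the median is too short by 0 to 1.1 h at 1% and by 0 to 5.8 h at 5%. It does not move when the stops come after the median.

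**Step 3: stops spread over time.** Lognormal recovery, median 96 h, log-SD 0.8, last entries uniform over 24 to 120 h, read at 312 h (Day 13). With G(t) the proportion of the share f still recording, and g(t) the recovery density of the others, the Kaplan-Meier hazard is (1 − f)g(t)/[(1 − f)S(t) + fG(t)]. Integrating it gives:

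| Share f | Day 13, planned | Day 13, actual | Gap (points) | Median, planned | Median, actual | Gap (h) |
|---|---|---|---|---|---|---|
| 1% | 92.9% | 92.0% | 0.9 | 96.6 h | 97.0 h | 0.4 |
| 5% | 92.7% | 88.3% | 4.4 | 98.9 h | 101.2 h | 2.4 |
| 10% | 92.5% | 83.7% | 8.8 | 101.9 h | 107.4 h | 5.5 |

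Here f counts only subjects who stop before the event. If it counts everyone with a poor course, some of whom alleviate before stopping, the Day 13 gap shrinks to about 3 points at 5% and 6 points at 10%.

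**Step 4: counts of subjects.** In simulation (Weibull, median 96 h, stops at 12 to 72 h), one such subject overstates end-of-follow-up recovery by 0.8 points with n = 120 and 1.2 points with n = 80. Six overstate it by 4.9 and 7.4 points.

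**Step 5: comparison with sampling error.** In the lognormal model the standard error of the median with n = 120 is 0.5/(√120 × 0.3989/(0.8 × 96)), about 8.8 h, well above the shifts at 1% and 5%. For the Day 13 share it is √(0.927 × 0.073/120), about 2.4 points, which the 4.4-point gap at 5% exceeds.

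**The case against.** The case for leaving the rule alone has real content.

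- **Consequence.** The primary endpoint is safety. These endpoints are secondary and descriptive, and no test or error rate depends on them.
- **Poor outcomes are reported elsewhere.** Complications and hospitalizations (Table 14.2.7), serious adverse events (Table 14.3.1.5), reasons for discontinuation (SAP 5.1) and diary completion (Table 14.1.5) are all summarized. A reader might infer that the rule hides the outcome the study exists to describe. The documents do not support that.
- **How often it happens.** Admission and pneumonia are not withdrawal criteria in Protocol 8.3, caregivers may complete the diary, and Protocol 8.2 excludes illness that is already complicated. A complication therefore need not end the record.
- **Most subjects without the event are unaffected.** Anyone who records to Day 14 without recovery is censored at the end of follow-up, which causes no bias. The permitted early stop in Protocol 10.2.2 requires 48 hours with all symptoms absent or mild, so it comes after the 21.5-hour event.
- **A broad repair would err the other way.** Protocol 8.2 and 11.1.1.2 recognize admission of elderly patients with influenza as institutional practice, and withdrawal for an unrelated adverse event says little about fever or symptoms. Counting all of these as not recovered would understate recovery.

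All of this stands, and it limits both the size of the point and the fix. It does not remove the bias: the separate tables do not feed the curves, and no planned analysis shows how far the curves depend on the censoring.

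**Conclusion.** The point holds in a limited form. Deaths, and withdrawals for worsening influenza or a complication, are censored as if uninformative, and this can only raise the estimated recovery. The late part of the curve is overstated by up to the share of such subjects: about 1 point at 1% and 4 to 5 points at 5%. The median moves by about 0.4 h and 2.5 h in the lognormal illustration, and by no more than 5.8 h at 5% in the Weibull scenarios tried. These sizes rest on assumed shares, assumed recovery distributions, and the assumption that none of these subjects recovers by Day 14.

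A reader might infer that the bias is known to be large, or largest in the oldest subjects. The documents give no rates overall or by age, so only the direction and the upper bound are established. The primary safety objective is untouched. The change is worth making because it is cheap and, with one arm, the curve is the finding.

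**What to change.** In SAP 3.3.4 and 5.2.2, for alleviation, fever and usual activities:

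1. Censor at Day 14, as not recovered, any subject who before the event dies, or whose recorded reason for withdrawal is worsening influenza or an influenza-related complication.
2. Keep last-assessment censoring for all other losses.
3. Add a sensitivity analysis that also keeps as not recovered those whose diary stops at an admission for worsening or a complication (not a routine institutional admission), or at withdrawal for another adverse event.
4. Add a second sensitivity analysis that uses the present rule throughout.
5. Report the number censored before Day 14, with reasons, by age group.

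The cost is SAP wording, a derived flag and some added output. The main rule needs only deaths and withdrawal reasons, and Protocol 8.3 already requires the reasons to be recorded. The first sensitivity analysis needs some case review, because the documents describe no field for why a diary stopped. Reported recovery may look slightly slower, and the rule is conservative for survivors who recover unrecorded. If no such subject occurs, the main estimates do not change.
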